6.2.2.1. Pre-administration Medications

In an effort to prevent IRR, on daratumumab administration days, patients will receive the following medications 1 to 3 hours prior to administration of daratumumab:

Acetaminophen (paracetamol)	650 - 1000 mg IV or per os (PO)
Antihistamine	Diphenhydramine 25 - 50 mg IV or PO, or equivalent (eg, cetirizine, fexofenadine, loratadine, clemastine, dexchlorpheniramine, or promethazine [note: avoid using IV promethazine]). Antihistamine may be discontinued after Cycle 2 at the investigator's discretion if the patient has side effects or does not tolerate.

Corticosteroids (Long-acting Intermediateacting) Administer 20 mg dexamethasone (or equivalent) prior to daratumumab injection during Cycle 1 (first 4 doses of daratumumab). Beginning in Cycle 2, corticosteroids may be tapered over 3 consecutive daratumumab injections to discontinuation at the investigator's discretion. The following dexamethasone taper should be used: 12, 8, and 4 mg over 3 daratumumab injections (for example, 12 mg on C2D1, 8 mg on C2D8, and 4 mg on C2D15, with no dexamethasone being given on C2D22 and beyond). Dexamethasone is given orally or intravenously prior to the first daratumumab injection and oral administration may be considered prior

daratumumab injection and oral administration may be considered prior to subsequent injections.

Half-life (Biologic) Approximate Glucocorticoid Equivalent Dose (mg) hours Intermediate Methylprednisolone 4 18-36 5 Prednisolone 18-36 Prednisone 5 18-36 4 18-36 Triamcinolone 0.6 - 0.75Long-acting Betamethasone 36-54 Dexamethasone 0.75 36-54

An equivalent intermediate-acting or long-acting corticosteroid may be substituted as shown below.

Leukotriene Predose administration of a leukotriene inhibitor (Montelukast 10 mg PO or equivalent) is optional on C1D1 and can be administered up to 24 hours before daratumumab injection as per investigator discretion.

If necessary, due to timing constraints, all oral pre-medications may be administered outside of the clinic on the day daratumumab is to be administered, provided they are taken within 3 hours prior to daratumumab injection.

6.2.2.2. Post-administration Medications

Consider administering low-dose oral methylprednisolone (≤ 20 mg) or equivalent on the day after daratumumab injection.

For patients with a higher risk of respiratory complications (eg, patients with mild asthma or patients with COPD who have an FEV1 <80% during screening or developed FEV1 <80% during the study without any medical history), the following medications should be considered following SC daratumumab injection:

- Antihistamine (diphenhydramine or equivalent)
- Leukotriene inhibitor (montelukast or equivalent)
- Short-acting β 2-adrenergic receptor agonist such as salbutamol aerosol
- Control medications for lung disease (eg, inhaled corticosteroids \pm long-acting β 2-adrenergic receptor agonists for patients with asthma; long-acting bronchodilators such as tiotropium or salmeterol \pm inhaled corticosteroids for patients with COPD).

In addition, these at-risk patients may be hospitalized for monitoring for up to 2 nights after an injection of daratumumab.

- If hospitalized, FEV1 should be measured and documented before discharge.
- If not hospitalized, then a follow up telephone call should be made to monitor the patient's condition within 48 hours after daratumumab injection.

Note: If the patient does not experience a significant medical event but is hospitalized overnight only for observation, then the hospitalization should *not* be reported as a serious adverse event.

Investigators may prescribe bronchodilators, H1-antihistamines, and corticosteroids that are deemed necessary to provide adequate supportive care if bronchospasm occurs after a patient is released from the hospital/clinic. If an at-risk patient experiences no major injection-related reactions, then these post-injection medications may be waived after 4 doses at the investigator's discretion.

Any post-injection medication will be administered after the injection has completed.

6.2.3. Management of Injection-site and Injection-related Reactions

6.2.3.1. Local Injection-site Reactions

Injection-site Reactions

In clinical studies, SC administration of daratumumab was associated with local injection site reactions, such as induration and erythema, in some patients. The reactions usually resolved within 60 minutes. Local ISRs should be managed per institutional standards.

6.2.3.2. Daratumumab Injection-related Reactions

Patients should be carefully observed during daratumumab administration. Trained study staff at the clinic should be prepared to intervene in case of any injection-related reactions, and resources necessary for resuscitation (eg, agents such as epinephrine and aerosolized bronchodilator, also medical equipment such as oxygen tanks, tracheostomy equipment, and a defibrillator) must be available at the bedside. Attention to staffing should be considered when multiple patients will be dosed at the same time.

Patients who experience AEs during daratumumab administration must be treated for their symptoms:

- Treatment with acetaminophen, antihistamine, or corticosteroids, may be administered as needed.
- IV saline may be indicated.
- For bronchospasm, urticaria, or dyspnea, patients may require antihistamines, oxygen, corticosteroids, or bronchodilators.
- For hypotension, patients may require vasopressors.

In the event of a life-threatening reaction (which may include pulmonary or cardiac events) or anaphylactic reaction, daratumumab-SC should be discontinued, and no additional daratumumab should be administered to the patient; and the patient must be permanently withdrawn from daratumumab treatment.

6.2.3.2.1. Injection-related Reactions of Grade 1 or Grade 2

If the investigator assesses a Grade 1-2 IRR to be related to administration of study intervention, then the daratumumab SC administration should be interrupted. When the patient's condition is stable, daratumumab SC administration may be restarted at the investigator's discretion. Refer to the SIPPM for further details regarding continuation of daratumumab SC administration.

If the patient experiences a Grade 2 or higher event of laryngeal edema or a Grade 2 or higher event of bronchospasm that does not respond to systemic therapy and does not resolve within 6 hours from onset, then the patient must be permanently withdrawn from daratumumab SC treatment.

6.2.3.2.2. Injection-related Reactions of Grade 3 or Higher

For injection-related reactions (other than laryngeal edema or bronchospasm) that are Grade 3, the daratumumab SC administration must be stopped, and the patient must be observed carefully until resolution of the adverse event or until the intensity of the event decreases to Grade 1, at which point the daratumumab SC administration may be restarted at the investigator's discretion. Refer to the SIPPM for further details regarding continuation of daratumumab SC administration.

If the intensity of the event returns to Grade 3 after restart of the daratumumab SC administration, then the patient must be permanently discontinued from daratumumab SC treatment.

For injection-related AEs that are Grade 4, the daratumumab SC administration must be stopped, and the patient permanently discontinued from daratumumab SC treatment.

6.2.3.2.3. Recurrent Injection-related Reactions

If a Grade 3 injection-related reaction (or Grade 2 or higher event of laryngeal edema or a Grade 2 or higher event of bronchospasm) recurs during or within 24 hours after a subsequent daratumumab administration, the patient must be permanently discontinued from daratumumab treatment.

6.3. Dose Delays and Dose Modifications

Dose modification of 1800 mg SC daratumumab (increase or decrease) is not permitted. Dose delay is recommended as the only method for managing daratumumab-related toxicities. Lenalidomide dose may be reduced, or the treatment schedule may be modified for the management of drug-related toxicities, per the investigator's discretion, according to lenalidomide prescribing guidelines.

Toxicities should be attributed, whenever possible, to a specific study drug so that treatment modifications can be made rationally. If multiple toxicities are attributed to an individual study

drug, dose adjustment (for lenalidomide only) should be made according to the guidelines for the most severe toxicity.

Modifications to the planned dosing regimen (lenalidomide only) should be overseen by medically-qualified study-site personnel (principal or sub-investigator unless an immediate safety risk appears to be present).

Study drug administration must be captured in the source documents and the eCRF.

6.3.1. Cycle Delay

Day 1 of a cycle should never be skipped, instead it should be considered a cycle delay. A minimum of 4 days between daratumumab doses must be observed.

On the first day of each new treatment cycle and before each daratumumab dose, the patient will be evaluated for possible toxicities that may have occurred after the previous dose(s). Toxicities are to be assessed according to National Cancer Institute-Common Terminology Criteria for Adverse Events (NCI-CTCAE), Version 5. Dose modifications (for lenalidomide only) or delays will be made based on the toxicity experienced during the previous cycle of therapy or newly encountered on Day 1 of a cycle.

The study treatment must be held if any of the following criteria below are met, to allow for recovery from toxicity, regardless of relationship to daratumumab or lenalidomide.

Administration of daratumumab may be restarted upon recovery from toxicity to Grade 2 or baseline, with the exception that Grade 2 laryngeal edema or Grade 2 bronchospasm must be fully recovered.

The parameters in Table 3 must be met on the first day of a new cycle (ie, the following represent baseline inclusion criteria levels).

Laboratory Parameter	Requirements Before Each Study Drug Administration
Absolute neutrophil count	$\geq 1.0 \times 10^9/L$
Platelet count	\geq 75×10 ⁹ /L
Hemoglobin	≥7.5 g/dL (≥4.96 mmol/L)

 Table 3:
 Re-treatment Criteria Before the Start of Each Cycle

Any dose holds of more than 28 days due to toxicity will result in permanent discontinuation of daratumumab. If a patient permanently discontinues study treatment(s), procedures should be performed as outlined in Section 10.2.1.

If the above parameters are not met, the start of the next cycle will be held for a minimum of 1 week and a maximum of 28 days until recovery to the specified levels. During the cycle delay, daratumumab and lenalidomide must be held. Dose holds of more than 28 days for other reasons should be discussed with the sponsor. If a dose delay occurs, then pharmacokinetic and

pharmacodynamic assessments should be performed on the actual day of study drug administration, not on the original scheduled administration day.

A study drug dose held for more than 3 days from the per-protocol administration date for any reason other than toxicities suspected to be related to daratumumab should be brought to the attention of the sponsor at the earliest possible time. Patients missing \geq 3 consecutive planned doses of study drug for reasons other than toxicity should be withdrawn from treatment, unless, upon consultation with the sponsor and the review of safety and efficacy, continuation is agreed upon.

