Hematology and serum chemistry*	x	 Hematology: Lenalidomide only arm: D1 of every cycle, ie, C1D1, C2D1, C3D1, C4D1, C5D1, C6D1, C7D1, C8D1, C9D1, C10D1, C11D1, C12D1, etc, up to C36D1. Lenalidomide + Daratumumab Arm: D1, D8, D15, D22 of Cycles 1 and 2; D1, D15 of Cycles 3, 4, 5, and 6; D1 of every cycle from C7 onwards (ie, C7D1, C8D1, C9D1, C10D1, C11D1, C12D1, C13D1, C14D1, C15D1, C16D1, etc.) Serum chemistry: Lenalidomide only arm: D1 of Cycles 1 through 6 (ie, C1D1, C2D1, C3D1, 	x	-	 On-site or accredited local laboratory must be used for hematology laboratory assessments. Results of local hematology tests must be evaluated before each study treatment administration to guide treatment decisions. Hematology panel to include: Hgb, WBCs with absolute neutrophils and lymphocytes, RBCs, and platelet count. Serum chemistry panel to include: Sodium, potassium, serum creatinine and creatinine clearance (CrCl) (must be calculated as described in Section 9.2.2), glucose, AST, ALT, total bilinubin, alkaline phosphatase, BUN, calcium and albuminadjusted calcium (see Section 9.2.3), and albumin. Note that albumin and serum calcium corrected for albumin will also be obtained on C1D1 from the central laboratory as described below under Disease evaluations, laboratory evaluations.

		STUDY PHA	SES/VISI	rs ^a	
Procedure	SCREENING	Maintenance (Cycles 1 – 36)	ЕОТ	Follow-up (from the date of last study treatment until the end of study)	Notes
		C4D1, C5D1, C6D1), and every 3^{rd} cycle thereafter (ie, C9D1, C12D1, C15D1 C18D1, C21D1, C24D1, C27D1, C30D1, C33D1 and C36D1) Lenalidomide + Daratumumab arm: D1, D8, D15, D22 of Cycles 1- 2; D1, D15 of Cycles 3-6; D1 of every 3^{rd} cycle thereafter (ie, C9D1, C12D1, C15D1, C18D1, C21D1, C24D1, C27D1, C30D1, C33D1 and C36D1)			
		On C1D1 and D1 of subsequent cycles, there is no need to repeat the tests if performed within the past 3 days. In addition, tests may be repeated as clinically indicated. Results must be evaluated before each daratumumab administration or beginning of new cycle of lenalidomide administration.			

		STUDY PHA	SES/VISI	TS ^a	
Procedure	SCREENING	Maintenance (Cycles 1 – 36)	ЕОТ	FOLLOW-UP (FROM THE DATE OF LAST STUDY TREATMENT UNTIL THE END OF STUDY)	NOTES

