- 4. Must have residual disease as defined by detectable MRD (Adaptive Biotechnologies' NGS-based MRD assay). If this assay was conducted post ASCT as part of institutional procedures and MRD results are available during screening, then patients who were MRD positive at 10⁻⁵ based on the existing NGS test result are also eligible to participate in the study (such patients will NOT be required to undergo MRD assessment by NGS again at the time of screening).
- 5. Must have an ECOG performance status score of 0, 1, or 2 (see Section 9.2.1).
- 6. Must have pretreatment clinical laboratory values meeting the following criteria during screening (laboratory tests should be repeated if not done within 3 days of C1D1):

Adequate bone marrow function:

- a. Hemoglobin ≥7.5 g/dL (≥4.65 mmol/L). Prior red blood cell (RBC) transfusion or recombinant human erythropoietin use is permitted, however transfusions are not permitted within 7 days of randomization to achieve this minimum hemoglobin count.
- b. Absolute neutrophil count $\geq 1.0 \times 10^9$ /L. Granulocyte colony stimulating factor use is permitted.
- c. Platelet count $\geq 75 \times 10^{9}$ /L for patients in whom < 50% of bone marrow nucleated cells are plasma cells. Otherwise, $\geq 50 \times 10^{9}$ /L (transfusions are not permitted within 7 days of testing to achieve this minimum platelet count).

Adequate liver function:

- a. Aspartate aminotransferase ≤ 2.5 folds of the upper limit of normal (ULN).
- b. Alanine aminotransferase ≤ 2.5 folds of the ULN.

c. Total bilirubin ≤2.0 folds of the ULN (except in patients with congenital bilirubinemia, such as Gilbert syndrome, direct bilirubin ≤2.0 folds of the ULN)

Adequate renal function:

- a. Estimated creatinine clearance ≥30 mL/min. Creatinine clearance may be calculated using Cockcroft-Gault, estimated glomerular filtration rate (Modification of Diet in Renal Disease [MDRD]), or Chronic Kidney Disease Epidemiology Collaboration (CKD-EPI) formula; refer to Section 9.2.2.
- b. Corrected serum calcium $\leq 14 \text{ mg/dL}$ ($\leq 3.5 \text{ mmol/L}$) or free ionized calcium $\leq 6.5 \text{ mg/dL}$ ($\leq 1.6 \text{ mmol/L}$); refer to Section 9.2.3.
- 7. If a female:

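### Table 3 of the protocol gives 4.96 mmol/L as the equivalent of the 7.5 g/dL haemoglobin re-treatment threshold; it should be 4.65 mmol/L, as in the inclusion criterion.

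*Protocol*

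**What the plan says.** The haemoglobin threshold appears twice in the current protocol text, each time in g/dL with a mmol/L equivalent in brackets.

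- Section 4.1, Inclusion Criteria, adequate bone marrow function, item a: "Hemoglobin ≥7.5 g/dL (≥4.65 mmol/L".
- Section 6.3.1, Cycle Delay, Table 3 (re-treatment criteria): "≥7.5 g/dL (≥4.96 mmol/L".

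The sentence introducing Table 3 ties the two together: it says that "the following represent baseline inclusion criteria levels".

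Table 3 is a dosing rule. If its levels are not met on Day 1, "the start of the next cycle will be held for a minimum of 1 week and a maximum of 28 days". Both drugs are affected: "During the cycle delay, daratumumab and lenalidomide must be held".

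On where haemoglobin is measured, the hematology row of the Time and Event Schedule – Part 1 says: "On-site or accredited local laboratory must be used for hematology laboratory assessments". Neither document fixes a reporting unit.

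**The concern.** The same 7.5 g/dL is converted to two different mmol/L values, although the protocol says that the two thresholds are the same. At least one conversion is therefore wrong, and the Table 3 row contradicts itself: a patient can pass it in one unit and fail it in the other.

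At stake is whether a cycle starts. A site that works from the bracketed figure would apply a stricter rule than intended and would hold both daratumumab and lenalidomide in patients who should be treated. Section 6.3.1 also requires permanent discontinuation of daratumumab after a toxicity hold of more than 28 days. A patient whose haemoglobin stayed in the disputed band could in principle reach that point while meeting the g/dL criterion throughout.

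There is also a reporting side. SAP Section 4.3 summarises cycle delays with their reasons, and SAP Section 4.4 summarises major protocol deviations. Whether a given dose or delay followed Table 3 should not depend on which half of the row was read.

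**Working it through.** **Inputs**

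- Inclusion threshold (Section 4.1): 7.5 g/dL, printed as 4.65 mmol/L.
- Re-treatment threshold (Section 6.3.1, Table 3): 7.5 g/dL, printed as 4.96 mmol/L.
- Minimum hold (Section 6.3.1): 1 week. Cycle length: 28 days.

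**Formula:** mmol/L = k × g/dL, where k is a fixed conversion factor. The documents do not state k, but each printed pair implies one.

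**Step 1: the factor implied by each pair**

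- Section 4.1: 4.65 / 7.5 = 0.620. Allowing for rounding of 4.65, the range is 4.645 / 7.5 = 0.6193 to 4.655 / 7.5 = 0.6207.
- Table 3: 4.96 / 7.5 = 0.661, which lies well outside that range. Rounding does not explain the difference.

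**Step 2: try to reproduce Table 3's figure**

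- With k = 0.620: 7.5 × 0.620 = 4.65, not 4.96.
- With k = 0.6206, the usual haemoglobin monomer factor (an assumption, since the documents give none): 7.5 × 0.6206 = 4.65.
- With k = 0.1551, a tetramer factor (also an assumption): 7.5 × 0.1551 = 1.16.

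None of these gives 4.96.

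**Step 3: what 4.96 mmol/L corresponds to**

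- With k = 0.620: 4.96 / 0.620 = 8.0 g/dL.
- With k = 0.6206: 4.96 / 0.6206 = 7.99 g/dL.

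So 4.96 is the equivalent of a round 8.0 g/dL. It may have been carried over from a threshold of 8.0 g/dL, but that is inference.

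**Step 4: size of the error**

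- 4.96 − 4.65 = 0.31 mmol/L.
- 4.96 / 4.65 = 1.067, so the printed figure is 6.7% too high.
- In g/dL: 8.0 − 7.5 = 0.5.
- Affected band: 7.5 to below 8.0 g/dL, or 4.65 to below 4.96 mmol/L.

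**Step 5: example and consequence**

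- A patient at 7.6 g/dL has 7.6 × 0.62 = 4.71 mmol/L. This passes the g/dL half of the row and fails the mmol/L half.
- The shortest resulting hold is 7 days, and 7 / 28 = 25% of a cycle length.

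**The case against.** The arithmetic is not in dispute. The case on the other side is that the error has little practical weight.

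- **The effect is conditional.** Table 3 leads with g/dL, which is correct, and mmol/L appears only in brackets. The sites are in the United States and Canada, and nothing in the documents shows that any laboratory reports haemoglobin in mmol/L. This stands. The harm is possible, not shown, and the number of patients cannot be estimated.
- **The direction is safe.** The wrong figure is stricter than intended, so it cannot lead to dosing below 7.5 g/dL. It touches neither eligibility nor the primary endpoint definition, alpha or power. This also stands.
- **A held week is a delay.** Sections 6.3.1 and 6.3.2.2 treat a missed Day 1 as a shift of the whole cycle, not a skipped dose. The 25% is therefore time off treatment while the cycle waits, and should not be read as a quarter of a cycle's doses lost.
- **Table 3 does not mirror the inclusion criteria perfectly.** Section 4.1 allows platelets down to 50 × 10⁹/L when at least half of the marrow nucleated cells are plasma cells, while Table 3 lists only 75 × 10⁹/L. The stated link is looser than it sounds. For haemoglobin this changes nothing, because the g/dL value is identical in both places and only its conversion differs.

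These points limit the consequence. They do not supply a reading under which 4.96 is right, nor a reason to leave a wrong number in a mandatory dosing table that offers mmol/L as a usable unit.

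**Conclusion.** The concern holds. The 4.96 mmol/L in Table 3 is wrong and 4.65 mmol/L was meant. This rests on the protocol's own conversion in Section 4.1 and on its statement that Table 3 repeats the inclusion levels; the usual conversion factor, taken as an assumption, agrees.

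The practical effect exists only where a site applies the mmol/L figure. There, patients in a 0.5 g/dL band would have both drugs held for at least a week without need. Where g/dL is used there is no effect. This is a definite error with a conditional and cautious consequence, and it should be corrected because it sits in a rule that decides whether treatment is given.

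**What to change.** In Table 3 of Section 6.3.1, replace the bracketed 4.96 mmol/L with 4.65 mmol/L. Leave 7.5 g/dL in both places and leave the inclusion criterion in Section 4.1 unchanged. Tell sites of the correction.

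The cost is a one-figure change, by clarification letter or in the next amendment. If the sponsor can confirm that every site laboratory reports in g/dL, waiting for the next amendment is enough; otherwise a letter is the safer route. No analysis, sample size or SAP text needs to change.

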6.3.2. Daratumumab

6.3.2.1. Daratumumab Dose Modification

Individual dose modification of daratumumab is not permitted, but dose delay is recommended as the primary method for managing daratumumab-related toxicities, as described in Sections 6.2.3 and 6.3.2.2.

6.3.2.2. Daratumumab-related Toxicity Management

Refer to Section 6.2.3 for details on management of daratumumab injection-related reactions.

If any of the following criteria are met and the toxicity is more than expected for lenalidomide or underlying multiple myeloma, daratumumab injection must be held to allow for recovery from toxicity. If attribution is unclear, then daratumumab should be held until recovery from toxicity as noted below.

The criteria for a dose delay are:

- Grade 4 hematologic toxicity, except for Grade 4 lymphopenia
- Grade 3 thrombocytopenia with bleeding
- Febrile neutropenia
- Neutropenia with infection, of any grade
- Grade 3 or higher non-hematologic toxicities with the following exceptions:
 - Grade 3 nausea that responds to antiemetic treatment within 7 days
 - Grade 3 vomiting that responds to antiemetic treatment within 7 days
 - Grade 3 diarrhea that responds to antidiarrheal treatment within 7 days
 - Grade 3 fatigue that was present at baseline or that lasts for <7 days after the last administration of daratumumab
 - Grade 3 asthenia that was present at baseline or that lasts for <7 days after the last administration of daratumumab

Administration of daratumumab may be restarted upon recovery from toxicity to Grade 2 or baseline, with the exception that Grade 2 laryngeal edema or Grade 2 bronchospasm must be fully recovered. Other than on Day 1 of a cycle, if any "within-cycle" daratumumab administration does

not commence within the prespecified window of the scheduled administration date (Table 4), then the dose will be considered a missed dose. Administration may resume at the next planned dosing date.

Daratumumab Dosing Frequency	Dose Missed	Dosing Resumption
Weekly	>3 days	Next planned weekly dosing date
Every 2 weeks	>7 days	Next planned every-2-weeks dosing date
Every 4 weeks	>21 days	Next planned every-4-weeks dosing date

 Table 4:
 Daratumumab-related Toxicity Management

A missed dose will not be made up. Delay of Day 1 drug dosing in any given cycle should not result in a skipped dose but should lead to a delay of the entire cycle instead. A minimum of 4 days between daratumumab doses must be observed.

If a dose is delayed, then the dates of all subsequent doses must be adjusted. If a dose delay occurs, then blood samples should be collected on the actual day of study drug administration, not on the original scheduled drug administration day. Any adverse event deemed to be related to daratumumab that requires a dose hold of more than 28 days will result in permanent discontinuation of daratumumab, unless, upon consultation with the sponsor and the review of safety and efficacy, continuation is agreed upon.

